8.6.2.1 Bleeding Pattern

- Menstrual bleeding pattern can be seen as a noninvasive marker for endocrine status in the studied cycle (33).
- The information on menstrual bleeding will be derived from Item 4 in the ESD (see Section 8.1.1.1).
- Cycle length and bleeding duration as well as an average intensity will be calculated.

8.6.2.2 Diameter of Ovarian Follicles

- Throughout the cycle, the diameter of the largest healthy follicles, with the exception of the dominant follicle, does not exceed on average 6 mm during the follicular phase and 4 mm during the luteal phase. The dominant follicle has a linear daily diameter growth of 2–3 mm per day, and at the moment of ovulation, the diameter of the dominant follicle is 18–27 mm.
- During the ultrasound examination (see Section 8.2.1), ovarian follicles should be monitored. The size of the largest follicle (if mean diameter > 10 mm) as well as presence of a ruptured follicle or corpus luteum should be recorded in the eCRF.
- Follicles larger than 18 mm, ruptured follicles, as well as structures identified as corpus luteum will be indicative of an ovulatory cycle.

27 JAN 2022 Page: 64 of 99

8.6.2.3 Serum Progesterone

Serum progesterone will be investigated from blood samples at each visit. Progesterone level ≥ 3 ng/mL (9.5 nmol/L) will be considered indicative of a recent ovulation (33, 34).

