The chosen stratification factors are region (China, Japan and rest of the world) and type of diagnosis (surgically vs clinically [for Japanese participants only]).

Pre-Intervention period

The duration of the pre- intervention period should be kept to a minimum. In rare cases it may not be feasible to complete the pre-intervention period within 35 days. In these cases the pre-intervention period may be extended over 35 days with prior approval from Sponsor, on case by case basis.

27 JAN 2022 Page: 31 of 99

Double-blind Intervention Period

The randomization and the start of intervention will take place on two different visits in order to supply the study drug per shipment on demand. To have a synchronized start of intervention with menstrual cycle, Visit 2 should be scheduled between Day 8 and Day 15 of the menstrual cycle.

Intervention period for primary analyses is 84+3 days.

Follow-up Period

The follow-up period will last for at least 90 days (13 weeks) for all study participants randomized to blinded treatment. Participants randomized to the open label elagolix arm will have a follow-up period of at least 38 days (5 weeks) after the last dose of study intervention.

Interim Analysis

Interim analyses may be performed after approximately 50% of the study participants have completed the 12-week intervention period in order to plan subsequent studies.

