8.6.2 Biomarkers Related to Ovarian Activity

Regular menstrual cycles are considered relevant indicators of reproductive health in women and changes may impact the quality of life. In order to demonstrate that BAY 1817080 has no effect on the menstrual cycle and ovarian activity, parameters indicative of ovarian activity will be assessed in this study.

Following parameters will be taken into account to assess ovarian activity:

- Regular menstrual bleeding
- Serum progesterone >3 ng/mL

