10.2 Appendix 2: Clinical Laboratory Tests

- The tests detailed in Table 10–1 will be performed by the central laboratory.
- Local laboratory results are only required in the event that the central laboratory results are not available in time for either study intervention administration and/or response evaluation. If a local sample is required, it is important that the sample for central analysis is obtained at the same time. Additionally, if the local laboratory results are used to make either a study intervention decision or response evaluation, the results must be recorded.
- Protocol-specific requirements for inclusion or exclusion of participants are detailed in Section 5 of the protocol.
- Blood samples for testing of liver parameters, i.e., AP, ALT (GPT), AST (GOT), Gamma-GT, and total bilirubin, should be taken as specified in the SoA. These visits are not to be performed in participants randomized to the active comparator elagolix.
- Additional tests may be performed at any time during the study as determined necessary by the investigator or required by local regulations.
- For pregnancy tests, see the SoA Section 1.3 and Section 8.3.5
- ATIII activity: Increases up to 30% above baseline value were observed in healthy subjects and chronic cough patients in study 18184. Since there is no established clinical relevance linked to increased ATIII activity in medical literature, it is concluded that at this stage of development, the increase in ATIII activity can be considered as not clinically relevant. Screening ATIII results will be available to the investigator/sites as soon as measured and reported by the central laboratory. Considering the potential for unblinding participants receiving active treatment with BAY 1817080, the results of ATIII measures at the following visits will not be communicated to study teams nor investigators until after unblinding of the study.

27 JAN 2022 Page: 76 of 99

Table 10–1: Protocol-Required Safety Laboratory tests

Panel	Parameters	Time point(s)	Comment
Safety parameter			
Biochemistry	Albumin	Visits 1a, 2-7	eGFR (MDRD
	Calcium		formula) calculation
	Magnesium		needed for Visit 1a
	Creatinine		only
	Cystatin C		
	Phosphorus		
	Potassium		
	Sodium		
	Total protein		
	Blood urea nitrogen		
	Alkaline phosphatase		
	ALT	 	
	AST		
	GGT		
	Total bilirubin		
	Total bile acids		
	Lipase		
	Pancreatic α-amylase		
	Non-fasting glucose		
	Total cholesterol		
	HDL-cholesterol		
	LDL-cholesterol		
	Triglycerides		

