4.5 Data Rules

Definition of Baseline

In general, baseline is defined as the last available measurement before start of treatment.

The 28-day baseline period for the ESD items is the last 28 days before start of treatment (e.g. -1 to -28). In case these contain less than 15 available entries, the baseline value will be given by the last 28 consecutive days before the start of treatment with at least 15 non-missing values (e.g. -2 to -29, -3 to -30, -4 to -31 and so on).

In addition, for daily measurements, if baseline and screening periods overlap, all the overlapping measurements will be considered as baseline data.

Definition of Post Baseline

In general, post baseline is defined as the first available measurement after start of treatment. Intervention period is 84 days, capturing 3 menstrual cycles of 28 days on average. As defined in Section 4.3.2, the 28-day mean of an item asking for pain can be derived if at least 15 non-missing entries are available.

Therefore, a post baseline value will be given by 28 consecutive days starting from end of treatment and counting backwards (e.g. day 84 to day 57 will be cycle 3). If a participant does not have 3 full available cycles, the count will start from the last available full cycle with at least 15 non-missing entries available (e.g. if two cycles are available, the count will start from day 56 to 29).

If a participant has 87 days of measurements, the first 3 measurements on day 1,2 and 3 will be discarded.

In addition, if a participant has more than 87 days of measurement, each data collected after day 87 will be discarded.

(Absolute change from) Baseline

To calculate the absolute change from baseline, the baseline value will be subtracted from the post-baseline value of interest, i. e.,

$$\text{Absolute change} = \text{post baseline value} - \text{baseline value.}$$

PROs data rules

If the weekly EIS questionnaire is administered less than 3 days after starting either Week 1, Week 5, 9 or 13 after start of treatment, the collected questionnaires will be counted for the previous 28-day cycle.

For example if a participant has the questionnaire pushed on day 3 after starting her treatment period, the responses will be counted as baseline.

If the monthly EQ5D questionnaire is administered less than 3 days after starting either Week 1, Week 5, 9 or 13 after start of treatment, the collected questionnaires will be counted for the previous 28-day cycle.

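### On-treatment progesterone is not timed to the luteal phase, so it is weak evidence that BAY 1817080 leaves ovarian activity unaffected

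*Protocol*

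**What the plan says.** Protocol 8.6.2 gives the purpose of the ovarian measures: to "demonstrate that BAY 1817080 has no effect on the menstrual cycle and ovarian activity". It lists two parameters, regular menstrual bleeding and serum progesterone above 3 ng/mL. Protocol 8.6.2.3 adds that "Serum progesterone will be investigated from blood samples at each visit" and that "Progesterone level ≥ 3 ng/mL (9.5 nmol/L) will be considered indicative of a recent ovulation".

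Three other places fix when those samples are taken:

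- **Start of treatment.** Protocol 4.1: "Visit 2 should be scheduled between Day 8 and Day 15 of the menstrual cycle". Visit 2 is treatment Day 1.
- **Hormone visits.** Table 10-1 places estradiol and progesterone at Visits 1a to 7. After the first dose and during treatment, the Schedule of Activities marks the safety laboratory panel only at Visit 3 (Day 28 ±3), Visit 4 (Day 56 ±3) and Visit 5 (Day 84 +3).
- **Visits in between.** Visits 2a, 3a and 4a (Days 14, 42 and 70, each ±3) appear only in the liver row. Protocol 10.2 restricts that row: "Blood samples for testing of liver parameters, i.e., AP, ALT (GPT), AST (GOT), Gamma-GT, and total bilirubin". These visits are not done in the elagolix arm.

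The working cycle length is in SAP 4.5: "Intervention period is 84 days, capturing 3 menstrual cycles of 28 days on average". Neither document ties the progesterone sample to a cycle phase. The SAP has general laboratory summaries (6.4.4.1) and a bleeding-pattern analysis (6.4.4.2), but no analysis of the progesterone threshold or of ovulation rate.

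**The concern.** Progesterone shows ovulation only if blood is taken in the days after it. Here the start is synchronised to roughly mid-cycle and sampling repeats about every 28 days, which is the assumed cycle length. Most women are therefore sampled again before or around ovulation, when the value is low whether or not they ovulate. The visits that do fall in the luteal phase are drawn in all blinded arms but not assayed for progesterone.

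The aim is to show an absence of effect. A marker that often misses ovulation pushes the comparison towards no difference, which is the hoped-for answer. At stake is how much weight a finding of no difference in progesterone can bear.

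**Working it through.** The documents state no figure for luteal coverage, so there is none to reproduce.

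**Inputs from the documents.** Start on cycle Day S = 8 to 15; visit days and windows as above; 28-day cycle.

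**Assumptions not in the documents.** Luteal phase of 14 days; progesterone at or above 3 ng/mL from 2 to 12 days after ovulation; S and the day within each visit window uniform; every cycle ovulatory.

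**Step 1: 28-day cycle, by counting.** Cycle day at treatment day t is S + t − 1, reduced by 28. With window offset o, this is S − 1 + o at Visits 3, 4 and 5. So Visits 3 and 4 fall on cycle Day 4 to 17 and Visit 5 on Day 7 to 17.

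| Visit | Combinations of S and o | Luteal (after Day 14) | Positive window (Day 16–26) |
|---|---|---|---|
| 3 | 8 × 7 = 56 | 6 (11%) | 3 (5%) |
| 4 | 56 | 6 (11%) | 3 (5%) |
| 5 | 8 × 4 = 32 | 6 (19%) | 3 (9%) |
| 2a, 3a, 4a (each) | 56 | 50 (89%) | 41 (73%) |

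Averaged over Visits 3 to 5, (6/56 + 6/56 + 6/32)/3 = 13% are luteal, so 87% are not. In the positive window: (3/56 + 3/56 + 3/32)/3 = 7%.

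**Step 2: women with at least one positive sample, Visits 3 to 5.** Only S = 14 and S = 15 can contribute.

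- S = 15: 1 − (5/7)² × (2/4) = 0.745
- S = 14: 1 − (6/7)² × (3/4) = 0.449
- Over eight start days: (0.745 + 0.449)/8 = 0.149, or 15%

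**Step 3: variable cycles, by simulation** (200,000 women per scenario; mean 27 to 30 days, between-woman SD about 2 to 2.5, within-woman SD about 1.5 to 2).

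| Quantity | 28-day cycle | Variable cycles |
|---|---|---|
| Visit 3–5 samples outside luteal phase | 87% | about 56–76% |
| Visit 3–5 samples in positive window | 7% | about 17–36% |
| 2a/3a/4a samples in positive window | 73% | about 51–66% |
| Women with any positive, Visits 3–5 | 15% | about 30–56% |
| Women with any positive, all six visits | 96% | up to 99% |
| Single 28-day cycle positive, paired visits (2a/3, 3a/4, 4a/5) | 78% | about 80–81% |

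The result depends on cycle length. With fixed 29- or 30-day cycles no Visit 3–5 sample is in the window. With fixed 25- or 26-day cycles 97–100% of women have one.

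**Step 4: what this does to a comparison.** Illustration only: 50 women per arm, Fisher's exact test, two-sided 0.05, on any positive sample. Halved means that the detection proportion is halved.

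| Placebo detection | Power, complete suppression | Power, halved |
|---|---|---|
| 15% | 78% | 12% |
| 30% | about 100% | 35% |
| 40% | about 100% | 52% |
| 56% | about 100% | 77% |
| 97% (all six visits) | about 100% | over 99% |

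**The case against.** **Complete suppression would still show.** This stands for variable cycles. SAP section 3 expects slightly irregular cycles, and drift gives about 30 to 56% of women an informative sample. A reader might infer that the schedule cannot detect any effect, or that a suppressing dose would look like placebo. Step 4 does not support that for complete suppression, except where cycles are nearly fixed at 29 to 30 days or the positive window is narrower. Starting the window at 3 days after ovulation cuts the 28-day figure from 15% to about 6%, where power for complete suppression is also about 6%.

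**Timing is the same in every randomised arm.** True, and it disposes of another tempting inference. Visit 6 falls mostly in the luteal phase at a 28-day cycle, so low values on treatment followed by higher ones might be read as reversible suppression. Placebo follows the same calendar and would show the same rise. Equal timing prevents a false difference; it does not restore sensitivity.

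**Progesterone is not the only marker.** Daily bleeding data are the other listed parameter, and Protocol 8.6.2.2 counts a large or ruptured follicle or a corpus luteum as a sign of an ovulatory cycle. These help. But after the first dose, ultrasound on treatment is scheduled only at Visit 5, also around cycle Day 7 to 17.

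**Cycle phase is already acknowledged.** Protocol 8.6.1 calls for cycle-controlled reading of inflammatory biomarkers and says visits do not follow individual cycles. It does not extend this to the ovarian criterion, and adjustment cannot supply luteal samples that were not assayed. Separate biomarker plans (Protocol 9.4.6) may handle phase; they are not among the documents.

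**The trial was stopped.** Amendment 2 ended treatment, so new assays at on-treatment visits cannot help here unless stored blood exists. Early stopping also moves Visit 5 away from Day 84, and Steps 1 to 3 do not describe those women. Both points stand.

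**The measure is exploratory.** Ovarian activity is not a named endpoint in Protocol section 3, which limits the weight of the point.

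**Conclusion.** The concern holds as a limit on sensitivity. At a 28-day cycle about 87% of on-treatment progesterone samples are outside the luteal phase, and about 15% of ovulatory women have any informative one. With mean cycles of 27 to 30 days and assumed variability, the figures are about 56 to 76% and 30 to 56%. Regular 25- to 26-day cycles are an exception.

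A low value at Visits 3 to 5 therefore cannot be read as anovulation, and similarity to placebo on this criterion is weak support for the aim in 8.6.2. Partial suppression would often be missed; complete suppression probably would not be in a variable population. Bleeding pattern and the Visit 5 ultrasound compensate only in part.

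The timing rests on the documents. The percentages rest on cycle variability and a positive window that the documents do not give. The reading also depends on 8.6.2.3 excluding the in-between visits, as the Schedule of Activities and 10.2 indicate. If they were meant to be included, most of the problem would disappear.

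**What to change.** **For any protocol using this schedule.** In 10.2, Table 10-1 and 8.6.2.3, add progesterone to the blood already drawn at Visits 2a, 3a and 4a in treatment groups 1 to 4. Compare each BAY dose with placebo on any value at or above the threshold across the six on-treatment samples. Report the per-cycle proportion alongside. The 96 to 99% coverage applies to any of six samples over 12 weeks; a single 28-day cycle is covered in only about 78 to 81% of cases, so not every cycle can be classified.

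**For the data already collected.** Assign each sample a cycle day from the bleeding record (ESD item 4). Restrict or stratify the progesterone analysis by cycle phase. State in the report that low values at Visits 3 to 5 are not evidence of anovulation, and that similarity to placebo does not prove absence of effect.

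**Text.** Reconcile the strict inequality in 8.6.2 with the non-strict one in 8.6.2.3, and state whether sampling at each visit includes 2a, 3a and 4a.

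**Cost.** One extra assay on existing draws, a small added blood volume and a short amendment; no new visit or venepuncture. Elagolix participants have no in-between visits, so the improved criterion covers only BAY against placebo. The work on existing data costs programming time only.

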8.6.3 Sleep Quality and Activity Measurement

Investigation of sleep quality and activity is considered as an option for an additional, objectively assessed, marker demonstrating improvement of patient outcome; further, the degree of baseline sleep disturbance could predict the response to treatment.

Optional participation in a sleep quality and activity substudy will be offered to a subset of participants. This will be limited to certain countries at the sponsor's discretion.

In an exploratory biomarker analysis, different parameters characterizing sleep quality (e.g. total sleep time, sleep onset latency, sleep efficiency) and daily activity (e.g. number of steps taken, physical activity intensity, sedentary bouts) will be investigated retrospectively (see Section 10.8 for details).

In addition to the objective sleep monitoring by wearable, all participants will be provided a sleep questionnaire developed to assess pain associated sleep disturbance (for time points, refer to SoA).

Pain and Sleep Questionnaire three-item index (PSQ3)

PSQ3 is a three-item PRO assessing 'trouble falling asleep because of pain', 'frequency of awakenings by pain during the night' and 'frequency of awakenings by pain in the morning' on the visual analogue scale with one week recall period. The items of PSQ3 are also part of the Pain and Sleep Questionnaire (PSQ) and Chronic Pain Sleep Inventory (CPSI). The assessment of selected psychometric properties of PSQ-3 using the data from clinical studies in different chronic pain indications is reported by Ayearst et al (35). PSQ-3 questionnaire will be completed during the site visits in eDiary.

8.6.4 Other Biomarkers

In addition to the biomarkers described above, further biomarkers related to, e.g., the mode of action or the safety of the study intervention and similar compounds may be investigated. The same applies to further biomarkers deemed relevant to endometriosis and associated health problems. These investigations may include e.g. diagnostic, safety, pharmacodynamic, monitoring, or potentially predictive biomarkers.

8.7 Immunogenicity Assessments

Not applicable

8.8 Health Economics

Health-economic parameters are evaluated through PROs EQ-5D-5L and mWPAI (Section 8.1.1) to assess utility and activity/productivity impairment. Descriptive PRO analyses will be part of clinical report, additional economic analyses including country-specific cost and utility estimation are planned in a separate HEOR analysis and report.

27 JAN 2022 Page: 65 of 99

9. Statistical Considerations

9.1 Statistical Hypotheses

The objective of the primary analysis is the detection of a trend in the relationship between the dose of BAY 1817080 and the primary efficacy endpoint, and describing the dose-response-relationship to provide a dose for possible phase III studies. Thus, only the placebo group (0 mg of BAY 1817080) and the three active intervention groups of BAY 1817080 with corresponding doses d_j , j=1,...,4, will be used for the primary efficacy assessment. The objective will be pursued through the application of the MCP-Mod approach, because there is not enough prior knowledge to decide on a specific dose-response-model $f(d, \theta)$. The MCP-Mod method makes "use [of] multiple comparison techniques to choose the most likely [parametric model among a set of candidates] to represent the underlying dose-response curve" (36). It combines the flexibility of modeling with the robustness to model misspecification associated with multiple comparison procedures.

For the so-called proof of activity of BAY 1817080, at least one of the null hypotheses

$$H_{0m}: \sum_{j=1}^{4} c_{mj} f(d_j, \boldsymbol{\theta}_m) = 0,$$

 $\sum_{j=1}^{4} c_{mj} = 0$, belonging to model m has to be rejected. The contrast coefficients c_{mj} are chosen such that they maximize the local power, i. e. the probability for rejecting the null hypothesis H_{0m} under the one-sided alternative hypothesis

$$H_{1m}: \sum_{j=1}^{4} c_{mj} f(d_j, \boldsymbol{\theta}_m) > 0.$$

Consequently, the null hypothesis H_{0m} states no trend in the dose-response-relationship (implying the overall null hypothesis of no trend in even one model) since the chosen dose-response-curves described in Section 9.4 are monotonically decreasing. The optimal contrast coefficients depend on the sample sizes in the end.

A more detailed description of the multiple comparison procedure modelling (MCP-Mod) approach and the models used will be given in Section 9.4.

9.2 Sample Size Determination

Approximately 840 participants will be screened to start study intervention in about 420 randomized participants for at least 50 participants evaluable for the primary analysis (i.e. included in the pPPS) per intervention group. The primary analysis will not include the participants enrolled based on visually-confirmed diagnosis, i.e. about half of the women randomized in Japan, nor all the participants randomized in China, who are mainly included to generate further data using the ESD in this population. Refer to Section 9.3 for further information of inclusion of participants into analysis sets.

If blinded data reviews indicate an unexpected high number of screening failures due to the COVID-19 pandemic, enrollment may be increased.

27 JAN 2022 Page: 66 of 99

Sample size calculations were performed for establishing evidence of a drug effect across the doses, that is, detecting a statistically significant dose response signal for the primary efficacy outcome in this study using the MCP-Mod approach. They are based on the following assumptions:

- change in mean EAPP under placebo after 12 weeks of -2.3
- maximum change in mean EAPP of -1.2 for BAY 1817080 over placebo
- standard deviation of 2.5 for all dose groups
- a set of plausible dose-response shapes including Emax and sigmoidal Emax models (chosen based on literature review and historic in-house data)
- random allocation of participants to dose groups according to a 1:1:1:1 ratio,

A sample size of 50 participants per dose groups will have appr. 90% power (averaged across the set of dose-response shapes) to demonstrate a dose- response relationship, using a one-sided test at a type I error rate of α =0.10.

Approximately 70 participants for primary analysis will be randomized to each treatment group to achieve 50 evaluable participants for each treatment group.

In addition, 28 participants from Japan with clinical diagnosis, as well as 28 participants from China will be randomized 1:1:1:1, but will not be included in the primary analysis.

Although not formally included in the sample size determination, the exploratory elagolix 150mg treatment group is planned to be of about the same size as the other treatment groups. As participants from Japan and China cannot be randomized to the elagolix 150mg arm, the randomization ratio outside of Japan and China will be 3:3:3:3:4 (Placebo:25 mg:75 mg:150 mg:elagolix). This will provide similar sizes of all treatment groups overall.

